The WELL Study (Wellness Education for Liver Health Study): Reducing liver disease in genetically predisposed adults

Version: 12-2-21
HUM00154361

Principal Investigator
[name]

Methodology:

We will examine the feasibility and acceptability of our four-month, online, dietary intervention among 40 adults with NAFLD from a high-risk subpopulation (rs738409-GG and rs738409-CG).

Participant recruitment, liver clinic evaluation, and inclusion

and exclusion criteria. We have already identified candidates from the Michigan Genomics Initiative using their electronic medical records including outpatient laboratory values that are homozygous for *PNPLA3* rs738409 and have elevated liver-function tests (median alanine aminotransferase above 35 international U/L). They have already consented to be re-contacted and are motivated participants interested in further research. The clinical characteristics of eligible participants are given in **Table 2**.

We will contact the pool of potentially eligible participants by sending them a postcard describing the study, either in an envelope or with mailing information directly on the postcard. We may also send a follow up letter or flyer describing the study, in an envelope with either a handwritten or a typed address. Potential participants may also receive a phone call. Interested participants will fill out a screening survey; study team members will review their medical records for exclusions and elevated liver function tests. Participants that appear to meet inclusion and do not have exclusion criteria, based on their survey and medical chart, (**Table 3**) and agree to participate will be referred to our liver clinic to be evaluated to rule out other causes of elevated liver function tests (such as medications or high levels of alcohol intake).

Participants who are taking blood glucose-lowering medications will be considered

Table 2. Clinical Characteristics of Michigan Genomics Initiative rs738409-GGs with elevated ALT

Characteristic	rs738409 GG
Participants	363
Male Sex	162 (45%)
Age	48 [27–65]
BMI	32 [27–37]
ALT	49 [42–65]

Values are given as either median and interquartile range or as N (%).

Table 3. Inclusion and exclusion criteria.

Inclusion	Exclusion
Age > 18	Non NAFLD causes of elevated liver function tests
MRI with liver steatosis but not cirrhosis	Pregnant
English speaking and access to internet	Recent decompensation/hospitalization

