Able to consent and follow directions	Weight loss medication or procedures planned
No physical limitations	Type 1 diabetes, cancer, heart failure, kidney failure, Cushing's syndrome
Physician approval to participate	Vegan, vegetarian, or other dietary restrictions
Rs738409 homozygote	Decompensated liver disease
Able to attend in-person appointments in Ann Arbor	Metal implants/inability to receive MRI

eligible for the trial. However, participants taking insulin will be excluded from participation. If the study team finds that recruitment is too slow and excluding insulin is too restrictive, participants taking insulin will be considered for enrollment. These participants will receive extra attention by study physicians in terms of medication management. See **Safety and medication management** section below.

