Many of these measurements are standard of care for non-alcoholic fatty liver disease and will be charged to the participant’s insurance. Baseline and follow up virtual visits, the baseline clinical liver MRI, and all baseline and follow up blood tests (with the exception of the excess serum, excess whole blood, and the fasting insulin tests) will be charged to the participant’s insurance. Participants will be informed of this during the consent process and will be encouraged to check their plans to ensure they have coverage. The study will cover the costs of all other measurements and materials.

Figure 1. Flowchart of intervention study.

NAFLD standard of care. All participants will receive care at our NAFLD liver clinic; we will provide state-of-the-art care of and resources about NAFLD to all participants. An information packet will be provided to all participants at their baseline office visit that includes: 1) NAFLD disease information including diagnosis, clinical manifestations, natural history, and treatments; 2) NAFLD physical activity recommendations including walking programs and physical activity logs; 3) weight tracking logs; and 4) resources for exercise programs. [name], with gastroenterology fellows working with her, will provide all medical care. Adverse events will be routinely queried at each clinic visit and the study physicians will be on call in the case of an adverse event. All participants will be taught a VLCD diets using our validated online program.

Participants will have a baseline virtual visit with [name] in the liver clinic and, if they appear eligible, they will come back for an MRI. After all baseline measurements are completed and if participants are still eligible, they will be enrolled in the 4-month online program. This program will include weekly lessons, mailed materials, and the support of a dietary coach. Details are outlined below:

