Safety and medication management. Participants will be asked in a weekly survey about health symptoms or adverse events they've experienced and to report any medication changes they've made. Participants who report symptoms will be reached by email as soon as possible by the study coordinator or diet coach. Participants may be called if the health event seems urgent or severe. For severe or long lasting symptoms, participants will be encouraged to reach out to their primary care physician. Participants who are taking some blood glucose-lowering medications (metformin, DPP-4s, GLP-1 agonists, and Thiazolidinediones (TZDs)) will continue their medications as normal. Participants taking all other glucose-lowering medications will be asked to stop taking these medications at the start of the trial (PCPs will be informed of this change when participants begin the trial). All participants will be asked in the aforementioned weekly survey about their highest and lowest fasted and postprandial (2 hours after eating) blood glucose levels over the previous week. If participants report low glucose (fasting below 70 mg/dL or postprandial below 110 mg/dL), they should reach out to their physician and follow self-management guidelines (sent to them as part of week 1's intervention materials). If participants report more than two weeks of high blood glucose (180 mg/dL), [name] [name] will reach out to participants via email or phone about management and reach out to participant PCPs.

Outcomes and analyses. After 16 weeks of the VLCD program, participants will complete a series of follow up measurements. Participants will complete a virtual follow up office visit, a follow up self-report survey, track their food, weigh themselves on the scale we sent them, take an at-home urine pregnancy test (if of childbearing potential), and return for a MRI-derived proton density fat fraction test. All final measurements should be completed within 4 weeks of completion of the program. Additionally, the second MRI will be conducted on research machines and charged to the study. Participants will also have a fasting blood draw. Follow up blood tests will include: complete blood count with differential, comprehensive metabolic panel, prothrombin time, fasting glucose, hemoglobin A1c, fasting insulin, and a serum lipid panel.

Statistical Design:

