Based on a previous, small, short-term trial without genetic biomarkers,[1] we expect patients enrolled in this program to lose 12% of their liver fat with a standard deviation of 6%. With a one-sample Wilcoxon test, this sample is 99% powered to detect such a decrease in MRI-derived fat fraction at $\alpha = 0.01$. Extrapolating from the epidemiological association of the rs738409-GG genotype with fatty liver in insulin-resistant patients,[2] the benefit in this group may be twice as high as in the general population (24%); if so, we would likewise be 99% powered to detect a reduction *significantly greater than* 12% at $\alpha = 0.01$.

One-sample Wilcoxon tests will likewise be used for post-program vs. baseline insulin resistance and body weight as secondary outcomes. We do not anticipate significant fibrotic differences after 4 months on this intervention, but will report pre-post liver fibrosis values. Baseline and post-program semi-structured interviews, as in Aim 1, will be used to assess satisfaction, adherence and dropout.

1. Reeve, B.B., et al., *Psychometric evaluation and calibration of health-related quality of life item banks: plans for the Patient-Reported Outcomes Measurement Information System (PROMIS)*. Medical care, 2007. **45**(5): p. S22-S31.
2. Craig, C.L., et al., *International physical activity questionnaire: 12-country reliability and validity*. Medicine & Science in Sports & Exercise, 2003. **35**(8): p. 1381-1395.
3. Kiernan, M., et al., *The Stanford Leisure-Time Activity Categorical Item (L-Cat): a single categorical item sensitive to physical activity changes in overweight/obese women*. International journal of obesity (2005), 2013. **37**(12): p. 1597.
4. Dalton, M., et al., *Preliminary validation and principal components analysis of the Control of Eating Questionnaire (CoEQ) for the experience of food craving*. European journal of clinical nutrition, 2015. **69**(12): p. 1313.
5. Tsenkova, V., J.M. Boylan, and C. Ryff, *Stress eating and health. Findings from MIDUS, a national study of US adults*. Appetite, 2013. **69**: p. 151-155.
6. Burgess, E., et al., *Profiling motives behind hedonic eating. Preliminary validation of the Palatable Eating Motives Scale*. Appetite, 2014. **72**: p. 66-72.
7. Norman, G.J., et al., *Reliability and validity of brief psychosocial measures related to dietary behaviors*. International Journal of Behavioral Nutrition and Physical Activity, 2010. **7**(1): p. 56.

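### Glucose-lowering drugs may be started, changed or stopped around baseline with no stable-dose rule, and the single-arm pre-post tests would mix any resulting change with the diet effect

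*Combined protocol and SAP*

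**What the plan says.** **Eligibility.** The recruitment section states: "Participants who are taking blood glucose-lowering medications will be considered" eligible. Insulin users are excluded at first, and that may be relaxed if recruitment is slow. Table 3 lists as an exclusion "Weight loss medication or procedures planned", without saying whether a GLP-1 agonist taken for glucose control counts. No criterion sets a minimum time on a drug or an unchanged dose before baseline.

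**During the programme.** Safety and medication management says of users of some drug classes: "metformin, DPP-4s, GLP-1 agonists, and Thiazolidinediones (TZDs)) will continue their medications as normal". Users of all other glucose-lowering drugs are asked to stop them at the start. The enrolment text after Table 3 reads differently: primary care providers are to be told that patients on any such drug except metformin may stop it. A weekly survey asks about medication changes. It sits under safety and has no stated use in the analysis.

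**Design and analysis.** The study is a "dietary intervention among 40 adults with NAFLD from a high-risk subpopulation", with no comparison group: "All participants will be taught a VLCD diets using our validated online program". Statistical Design tests the change in liver fat with a one-sample Wilcoxon test and adds: "One-sample Wilcoxon tests will likewise be used for post-program vs. baseline insulin resistance and body weight as secondary outcomes". No adjustment, stratification or sensitivity analysis for medication is given.

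**The concern.** A one-sample test of change credits everything that happens between the two measurements to the programme. Someone who started or raised the dose of a glucose-lowering drug shortly before screening meets every listed criterion. Any drug effect still developing at the baseline MRI then falls inside the measured change. The same applies to a change during follow-up, and to drugs stopped when the diet begins. With no control arm, there is nothing to subtract.

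Table 3 already treats weight-loss medication as a reason to exclude, so the protocol accepts that a drug can disturb these outcomes. It does not carry that reasoning through to the drugs that continue. At stake are the size of the effect attributed to the diet and the planned claim that the reduction in this genotype exceeds 12%.

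**Working it through.** **1. The plan's own figure.** Statistical Design expects participants to "lose 12% of their liver fat with a standard deviation of 6"%, and states: "With a one-sample Wilcoxon test, this sample is 99% powered to detect such a decrease", at alpha 0.01. It does not state whether the test is one- or two-sided, or whether the percentages are relative or absolute. With n = 40 and the Wilcoxon relative efficiency 3/π for normal data:

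power = Φ(δ√(n × 3/π)/SD − z) = Φ(12 × √38.2/6 − 2.576) = Φ(12.36 − 2.58), which exceeds 0.999 two-sided.

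One-sided, z = 2.326 and the result is the same. The 99% statement is met. The comparison of 24% with 12% is also a 12-point shift and has the same power if the SD stays at 6. The issue is therefore attribution, not power.

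**2. Shift in the mean.** If k of 40 participants are recent starters with drug effect D, the mean change moves by k × D/40. The documents give neither k nor D. I assume D = 10 to 30 points on the scale of the planned SD, with the whole effect falling after baseline.

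**3. Rejection with no diet effect.** Settings: n = 40, normal data, SD 6, zero diet effect, k participants shifted by D, exact two-sided signed-rank test at 0.01, 40,000 runs per cell. Ranges run over D = 10, 20 and 30.

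| Recent starters k | Mean shift (points) | Average shift of sample median | Rejection |
|---|---|---|---|
| 0 | 0 | 0 | 0.9-1.0% |
| 1 | 0.25-0.75 | 0.2 | 0.9-1.0% |
| 2 | 0.5-1.5 | 0.4 | 1.3-1.5% |
| 4 | 1-3 | 0.7-0.8 | 3-4% |
| 8 | 2-6 | 1.6-1.9 | 11-21% |

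Shorter runs with other seeds reached 22% for eight starters.

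**4. Smaller drug effects.** With D = 3 to 12 points and a random number of starters, rejection is 1.1-1.7% at an expected share of 5%, 1.2-4.7% at 10%, 2.0-17% at 20% and 4.5-47% at 30%. The upper ends here exceed those in the table partly because the number of starters varies from trial to trial.

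**5. The claim of exceeding 12%.** If the true diet effect is exactly 12, subtracting 12 from each change returns the situation in step 3. The same rejection rates apply, now as false claims that the reduction exceeds 12%.

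**6. Stopped drugs.** A participant who stops a drug at the start also changes treatment between the measurements, and the effect may run the other way. The documents do not say how many would stop or what would follow, so the net sign cannot be derived.

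**7. Power left after exclusions.** Under the plan's inputs, two-sided at 0.01, simulated power is above 0.999 with 15 analysed, 0.998 with 12, 0.987 with 10 and 0.84 with 8. Dropping some participants costs almost nothing for the main test.

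**The case against.** **Feasibility aim.** The stated purpose is feasibility and acceptability, and no single-arm pre-post study can separate diet from co-interventions. The activity packet and clinic care are equally inseparable. This is fair as to purpose, but Statistical Design still sets powered efficacy tests at 0.01, and medication is a co-factor that an eligibility line can limit.

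**Size.** Diabetes is not an inclusion criterion, so users may be few. With one or two recent starters the test behaves nearly as it should. The rank test also damps the disturbance: the median moves less than the mean. Someone who began a drug weeks before screening would have part of its effect in the baseline MRI already, because the MRI is scheduled two to four weeks after the virtual visit, which may itself fall up to a month after the consent call. All of this stands, and it makes the table a set of upper-leaning scenarios.

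**Existing checks.** Chart review, the clinic visit and primary care approval could reveal a recent start, but none applies a stability rule. The weekly survey cannot capture a start before the programme.

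**Stronger readings.** A reader might infer three things that the documents do not support:

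- That Table 3 flatly contradicts the continuation of GLP-1 agonists. The word *planned* can govern both medication and procedures, so this is an unresolved tension.
- That the bias must favour the diet. Some drugs are stopped at trial start, and the enrolment text leaves open whether GLP-1 agonists and TZDs continue at all.
- That the main result would be spurious. At the planned 12-point effect the test rejects almost always, with or without recent starters.

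**Conclusion.** The gap is real, but its size and net direction are unknown. The protocol sets no stable-dose requirement and makes no analytic allowance for medication, so drug starts, dose changes and stops are confounded with the diet. The rejection rates in the table rest on assumed drug effects, assumed numbers of starters, normal data and SD 6. They describe a problem that is negligible with one or two recent starters and material at about one participant in five. It bears on the effect estimate, on a small or null diet effect, and on the claim of exceeding 12%, not on the main test if the planned effect is true. It is worth correcting because the remedy is cheap.

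**What to change.** 1. **Eligibility.** Add to Table 3 that glucose-lowering drugs which continue must have been at an unchanged dose for a period, set by the sponsor, before the baseline MRI, weight and bloods. Allow later re-screening. Cost: one line, and delayed enrolment for some candidates.
2. **Data and sensitivity analysis.** At baseline, record each glucose-lowering drug, its start date and the date of its last dose change. Use these with the weekly survey, updated at the follow-up visit because final measurements may come up to four weeks after the programme. Pre-specify a repeat of the liver fat, weight and insulin-resistance analyses without participants who started, changed or stopped such a drug shortly before baseline or between baseline and follow-up. Excluding on-study changers alone would miss starts before baseline. Cost: a few baseline fields and one extra analysis, with little loss of power for liver fat.
3. **Consistency.** Reconcile the enrolment text (drugs other than metformin may be stopped) with Safety and medication management (GLP-1 agonists, TZDs and DPP-4s continue). State whether the weight-loss medication exclusion covers current GLP-1 agonist use. Which clinical rule applies is for the sponsor and investigators to decide. Cost: a text edit.

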Potentially eligible participants will complete a screening consent survey via Qualtrics. After consenting to screening activities, they will complete an online baseline survey concerning their general health and well-being, watch a short, informational video about the trial and answer several comprehension questions, and set up an appointment for a phone call with the study coordinator. Prior to the phone appointment, the study coordinator will send participants the full study consent via SignNow. During this appointment, the study coordinator will go over the full consent with participants, having them sign on SignNow when all questions are answered. After consenting, participants will schedule two appointments with the study coordinator. The first appointment will be a virtual visit with [name] at Michigan Medicine's Taubman Center liver clinic and the second will be a baseline liver MRI; participants will receive instructions to call and schedule their baseline MRI to ensure the schedulers have accurate safety information when scheduling the appointment. The virtual visit will be scheduled within one month of the phone call, the second will be scheduled two to four weeks after the first. Participants who elect to participate in the optional induced pluripotent stem (iPS) cell research will be asked to informally schedule a time to get their blood drawn at the Taubman blood draw clinic. This blood draw must take place at the hospital to ensure sample viability. Participants will choose a time on a weekday, ideally in the morning, within two weeks of their appointment with [name]. At the virtual visit, [name] will evaluate the full medical history and physical health. History will be evaluated for cardiovascular disease (angina, myocardial infarction, stroke, heart failure). If participants are not getting blood drawn for iPSC research, then they will proceed to a fasting blood draw at any MM Labs location (no appointment needed) within one to two weeks following this virtual visit. If participants are getting blood drawn for iPSC research and scheduled a time for their blood draw during their consent visit, then they will go to the Taubman Center blood draw clinic at the time of their appointment. A member of [name] team will either meet with participants when they arrive at the clinic to provide research tubes to the phlebotomist for the iPSC samples or will arrive immediately following the participant's blood draw to collect the samples. Blood tests will be drawn to assess (1) the cause of elevated liver function tests (complete blood count with differential; comprehensive metabolic panel; prothrombin time; C-reactive protein; erythrocyte sedimentation rate; hepatitis A, B, and C serologies; iron studies (iron level, iron binding capacity, percent transferrin saturation, ferritin); antinuclear antibodies; anti-LKM-1 antibodies, antimitochondrial antibodies; antismooth muscle antibodies; and alpha-1-antitrypsin levels), (2) diabetes (fasting glucose, fasting insulin, and hemoglobin A1c), and (3) dyslipidemia (serum lipid panel). Additionally, participants will have excess whole blood and serum drawn during their appointments. This serum (SST tube) will be transported to a lab in the University of Michigan's School of Public Health and tested for levels of an appetite suppressing hormone (growth differentiation factor: GDF15). For participants contributing blood for iPSC research, two tubes of whole blood (ACD solution A tubes or two CPT with sodium citrate tubes) will be drawn and transported to a lab within Medical Sciences Building II ([name] Lab). Participants may opt out of this step in the main study consent form. Also in the week following their virtual visit, participants must fill out an additional survey providing personal information, including their address (for mailed materials) and their primary care provider's name and phone number. Participants will also track their food for three days on the MyFitnessPal website or complete two 24-hour dietary recalls over the phone. The study team will reach out to the primary care providers of participants who have eligible blood tests. Primary care providers must approve their patient's participation before the subject is enrolled, within one month of first contact attempt. Primary care providers of participants who are taking blood glucose-lowering medications other than metformin will be advised that their patient may stop their medications as they begin the program to avoid risk of hypoglycemia. All primary care providers will be informed that their patient may reach out to them if they're experiencing symptoms or may need further medication adjustments.

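### The pooled pre-post insulin-resistance test mixes protocol-directed drug withdrawal with the diet effect for an unknown number of participants, and should not be read as a diet effect alone

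*Combined protocol and SAP*

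**What the plan says.** The study is a single-program "online, dietary intervention among 40 adults with NAFLD"; no control arm is described. Users of glucose-lowering drugs can enter: "Participants who are taking blood glucose-lowering medications will be considered" eligible. Insulin users are excluded at first, but if recruitment proves too slow "participants taking insulin will be considered for enrollment".

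The baseline blood panel, in the recruitment section of Methodology, includes "2) diabetes (fasting glucose, fasting insulin, and hemoglobin A1c". For participants not giving blood for stem-cell research, it is drawn "within one to two weeks following this virtual visit". No washout before this draw is described. The section on NAFLD standard of care fixes the order: "After all baseline measurements are completed and if participants are still eligible, they will be enrolled in the 4-month online program".

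Safety and medication management names four classes that continue: metformin, DPP-4s, GLP-1 agonists and TZDs. For the rest: "Participants taking all other glucose-lowering medications will be asked to stop taking these medications at the start of the trial". The same section has a weekly survey that records medication changes.

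Outcomes and analyses repeats fasting glucose, fasting insulin and HbA1c after the 16 weeks. Statistical Design then states: "One-sample Wilcoxon tests will likewise be used for post-program vs. baseline insulin resistance and body weight as secondary outcomes". It does not define insulin resistance, does not mention medication, and does not say whether the target is the diet alone or the program as delivered.

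**The concern.** A pre-post comparison without a control group attributes everything that changes between the two measurements to the intervention. Here the protocol itself changes one other thing, for some participants, between the two draws. If stopping a drug moves fasting insulin or glucose, it moves any index built from them.

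The bias could go either way. If withdrawal lowers the index, part of an apparent improvement is due to the drug change. If withdrawal raises it, a real diet effect is partly hidden. Insulin resistance is one of only two secondary outcomes given a named test, so a reader is likely to take its result as evidence about the diet. The data needed to separate the groups are already collected, but the analysis does not use them.

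**Working it through.** **Order of events**

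1. Baseline draw: during screening, on whatever drugs the participant takes (recruitment section).
2. Enrollment: only after all baseline measurements (NAFLD standard of care).
3. Drug stop: at the start of the trial (Safety and medication management). The recruitment section also places it at the beginning of the program.
4. Follow-up draw: after 16 weeks (Outcomes and analyses).

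Step 3 falls between the two values that are compared, so for anyone who stops a drug, observed change = diet effect + withdrawal effect. Nothing in Statistical Design separates the two terms.

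**The plan's own figure**

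The only power statement concerns liver fat: mean loss 12%, SD 6%, alpha 0.01, 99% power. The standardized effect is 12/6 = 2. At n = 40, both a normal approximation with Wilcoxon efficiency 3/π and simulation give about 100%, one- or two-sided, consistent with the stated 99%. This figure does not involve insulin resistance and is not affected by this point.

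**Size for insulin resistance (all values below are assumptions except n = 40)**

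The analyzed quantity is taken as the log ratio of follow-up to baseline, with SD 0.4. The test is a two-sided Wilcoxon signed-rank test at 0.01; the plan states 0.01 for liver fat and gives no level or sidedness for the secondary tests. All 40 participants are assumed to complete. A number k of them is shifted by withdrawal. Rates come from several thousand simulated trials per cell.

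*No diet effect, index falls on withdrawal.* The shift is log(0.7) = −0.36 (30% fall) or log(0.5) = −0.69 (50% fall). The apparent geometric-mean fall is 1 − 0.7^(k/40) or 1 − 0.5^(k/40).

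| k of 40 | Apparent fall | Chance of declaring a fall |
|---|---|---|
| 0 | 0% | about 0.5% |
| 2 | 2% to 3% | about 1% |
| 4 | 3% to 7% | about 2% to 3% |
| 8 | 7% to 13% | about 4% to 12% |
| 12 | 10% to 19% | about 11% to 35% |

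*Mixed directions.* With 4 participants down 30% and 4 up 40%, the shifts sum to 4 × (−0.36) + 4 × 0.34 = −0.08 on the log scale over 40 people. The false-declaration rate shows no inflation.

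*True 20% fall, index rises 40% on withdrawal.* Power is about 75% with none affected, about 55% with 4 and about 34% with 8.

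**Who is affected is itself unclear**

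In the recruitment section, primary care providers are advised that glucose-lowering drugs apart from metformin may be stopped. Safety and medication management lists four classes that continue. A participant on a DPP-4, GLP-1 agonist or TZD falls in the affected group under one passage and outside it under the other.

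**The case against.** **Few may be affected.** Recruitment is by genotype and ALT, Table 2 gives no diabetes or drug data, four drug classes continue, and insulin users are out unless recruitment is slow. If k is 0 there is no bias, and at k = 2 it is negligible. This stands. A reader might infer that the insulin-resistance result is likely to be a false positive. The documents do not support that: no count, no withdrawal effect and no direction is given, and the larger rates above need 8 to 12 people all shifting the same way.

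**The index is undefined.** That it is built from fasting glucose and insulin is an inference from the blood tests listed at both times. This also stands.

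**The planned test can be read as the effect of the whole program, drug rule included.** That is a legitimate target, and a reason to keep the test. But Statistical Design does not say so, and a reader would not know that drug changes are part of what is estimated.

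**A control arm would not necessarily help.** Correct: a control arm that kept its drugs would differ from the program arm in the same way. The problem is the unstated target and unused medication data, not only the lack of controls.

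**Why not restrict the test to people whose drugs did not change?** This is tempting but can add bias, because later changes can depend on response: reported low or sustained high glucose leads to contact with physicians, and providers are told adjustments may be needed. As an illustration with the settings above and a true 20% fall, suppose 8 participants continue a drug and those among them with better-than-average response have it reduced and so leave the test. The restricted test then shows a fall of about 17%, and its power drops from about 76% to about 52%. Restriction should therefore use drugs at baseline, and should supplement the planned test.

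**Conclusion.** The mechanism is established by the text: baseline draw, protocol-directed stop, follow-up draw, one pooled test. For participants who stop a drug, withdrawal and diet cannot be told apart in the planned analysis, so the pooled result should not be presented as the effect of the diet alone.

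The impact is not established. It ranges from none to material across the assumed scenarios and depends on the number affected, the withdrawal shift, its direction and the index used, none of which the documents give.

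The severity is minor. Insulin resistance is a secondary outcome in a 40-person feasibility and acceptability study. The documents do not support extending the point to the liver-fat power calculation.

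**What to change.** In Statistical Design:

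- Define the insulin-resistance index.
- Keep the planned test in all participants, and describe it as the effect of the program including its medication rule.
- Add a pre-specified analysis of insulin resistance in participants who at baseline take no glucose-lowering drug, or only drugs the protocol continues, and who do not use insulin. Membership is fixed at baseline, so it cannot depend on response.
- List participants with a protocol-directed stop separately, with baseline and follow-up values.
- Summarize later drug changes from the weekly survey.

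The recruitment section and the Safety and medication management section describe the affected drugs differently and must be reconciled, since the added analysis depends on that definition. No drug rule needs to change for the statistical fix.

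The cost is some added wording, with no new data collection. The added analysis has a smaller n: with 40 − 8 = 32 participants, power against a true 20% fall is about 62%, compared with about 75% at 40, under the same assumptions. The planned test keeps its full sample.
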